Improving CarE for Community Acquired Pneumonia (ICE-CAP)

Phase 1: Antibiotic Decision Support
Phase 2: Prognostic Decision Support

Principal Investigator

[name], MPH
Vanderbilt University Medical Center

Co-Investigators

Vanderbilt University Medical Center

[name]
[name], MPH
[name], MS
[name], PhD
[name]
[name], MS, MD
[name]
[name], MPH

University of Pittsburgh/Children's Hospital of Pittsburgh

[name]
[name]
[name]
[name], MS

Table of Contents:

1.0	Background
2.0	Rationale and Study Phases
3.0	Previous Human Studies
4.0	Study Design and Randomization
5.0	Inclusion/Exclusion Criteria
6.0	Screening/Enrollment
7.0	Study Procedures
8.0	Statistical Considerations
9.0	Risks to Participants
10.0	Privacy/Confidentiality Issues
11.0	Reporting of Adverse Events or Unanticipated Problems involving Risk to Participants
12.0	Study Withdrawal/Discontinuation
13.0	Follow-Up and Record Retention
14.0	References

Protocol Summary:

Children with pneumonia presenting to the ED at Monroe Carell Jr. Children’s Hospital at Vanderbilt or Children’s Hospital Pittsburgh at the University of Pittsburgh will be potentially eligible for study. During intervention periods, providers caring for enrolled children will be presented with a detailed decision support strategy that emphasizes management in accordance with national guideline recommendations. The anticipated study duration is 18 months for Phase 1 (P1) and 24 months for Phase 2 (P2). As this study does not include direct contact with enrolled subjects, there is no anticipated follow up.

Protocol Versions

Version	Date of Approval	Major Changes from Prior Version
1.0	Jul 15, 2018	-
2.0	Feb 8, 2019	Update study site; minor edits for clarity

1.0 Background

Pneumonia is the most common serious infection in childhood. In the United States (US), pneumonia accounts for 1-4% of all emergency department (ED) visits in children (3-28 per 1,000 US children per year)¹ and ranks among the top 3 reasons for pediatric hospitalization with >100,000 hospitalizations per year (15-22 per 100,000 US children per year)²⁻⁵. Pneumonia also accounts for more days of antibiotic use in US children’s hospitals than any other condition.⁶

Safely reducing inappropriate antibiotic use is critical to slow the progression of antimicrobial resistance, and childhood pneumonia is a key area where substantial improvements can be made. In the 2011 Pediatric Infectious Diseases Society/Infectious Diseases Society of America (PIDS/IDSA) pneumonia guideline, appropriate use of antibiotics was an important area of emphasis.⁷ For presumed bacterial pneumonia, recommendations emphasize the use of a single, narrow-spectrum antibiotic (i.e. amoxicillin or ampicillin). In children <6 years of age treated in the outpatient setting, the guideline recommended considering withholding antibiotics, recognizing that pneumonia in this population is most often caused by viruses. Both of these recommendations were graded as strong and supported by high-quality evidence.⁸⁻¹⁰ Nonetheless, in a large database study we conducted just prior to release of the 2011 guideline, use of broad-spectrum antibiotics was very common among children hospitalized with pneumonia, with substantial differences in antibiotic selection patterns among the various hospitals.¹¹ In that study, use of narrow-spectrum ampicillin was rare (<5%). High rates of broad-spectrum antibiotic use were also noted in a study of children with pneumonia treated and released from US EDs, with <30% of children receiving narrow-spectrum therapy.¹²

Emergency care for childhood pneumonia, including hospitalization rates, varies widely across the nation. A study examining hospital admission rates at 35 US children’s hospitals from 2009-12 showed marked differences in severity-adjusted pneumonia hospital admission rates (median 31%; range 19-69%)¹³. Extending these findings, Florin et al. detected great hospital-level variation in the use of diagnostic tests for children presenting to the ED with pneumonia.¹⁴ They reported that high test-utilizing hospitals had a

nearly 2-fold greater odds of hospitalization compared with low test-utilizing hospitals.¹⁴ Using the same database as Florin et al., we previously reported similar institutional variation in diagnostic test utilization in children hospitalized with pneumonia. The range across hospitals for even the most common diagnostic tests was very wide with some hospitals performing specific tests in <30% of children and others performing those same tests in >75% of children. We also demonstrated an association between high test-utilizing hospitals and increased average hospital length of stay.¹¹

Provider preferences and inaccurate risk perceptions contribute to differences in hospitalization rates. Within the Intermountain Healthcare System in Utah, Dean et al. exposed large differences in admission rates (range 38-79%) among 18 individual ED providers providing care for >2,000 adults with pneumonia.¹⁵ Differences were not explained by patient characteristics or illness severity and higher rates of hospitalization did not reduce hospital readmissions or mortality. In another multicenter study of 472 adults with pneumonia at <4% risk of 30-day mortality estimated using objective severity scores, providers overestimated the risk of mortality in 5% of outpatients (range across institutions 0-12%) and 41% of inpatients (range across institutions 36-48%).¹⁶ These studies suggest that risk perceptions are often inaccurate, and potentially lead to unnecessary or prolonged hospitalizations and intensive therapies. Similar studies have not been performed in children because no valid prognostic tools exist to reliably predict pediatric pneumonia severity.

2.0 Rationale and Study Phases

Extensive variation in both antibiotic use and hospitalization decisions is evident among clinicians caring for children with pneumonia, with high potential for avoidable harm. In our prior study, one-third of children were hospitalized for less than 48 hours and nearly 10% less than 24 hours. Some of these hospitalizations were likely unnecessary. Most of these children also received broad-spectrum antibiotic therapy instead of the narrow-spectrum agents recommended by the national guideline. Conversely, one-third of children admitted to intensive care were initially managed on a general ward—earlier transfer for more intensive therapy may have improved outcomes for some of these children. New strategies to inform decision making are needed, and the combination of risk stratification using objective tools and clinical decision support in the ED setting are innovative and promising approaches to achieve this goal.

Phase 1: *To test the hypothesis that electronic antibiotic decision support increases guideline-concordant antibiotic use compared with usual care in the ED.*

The primary outcome is the proportion of children exclusively receiving guideline-concordant 1st line antibiotic therapy during the first 24 hours of care (Table 1). Secondary outcomes include exclusive use of concordant antibiotic therapy for the entire episode, any use of concordant antibiotic therapy during the first 24 hours of care and for the entire episode, and ED revisits and hospitalizations within 72 hours and 7 days of the index discharge.

Phase 2: *To test the hypothesis that the delivery of severity information generated by our prognostic tool leads to more appropriate site of care disposition compared to usual care.*

The primary outcome is appropriate site of care disposition (Table 2). Surveillance for subsequent ED visits and hospitalizations to our institutions as well as escalation to higher levels of care will be captured within the EHR data extracted by the decision support application. Secondary efficacy and safety outcomes include the overall site of care disposition (ED discharge, ward, ICU), and ED revisits and hospitalizations within 72 hours and 7 days of the index discharge.

In these studies, conducted at two experienced academic centers, we will implement and evaluate an EHR-based clinical decision support application to promote antibiotic use in concordance with the 2011 PIDS/IDSA guideline in a pragmatic, cluster-randomized crossover trial (P1). Next, we will incorporate risk stratification using a previously developed prognostic tool into a second EHR-based decision support application, testing its impact on site of care disposition compared to usual care in a pragmatic randomized trial (P2). In both studies, all subjects will receive standard of care. Decisions regarding management, including antibiotic selection and site of care, will be at the discretion of the treating provider and will not be restricted or altered in any way. Thus, this study poses no greater than minimal risks to participants. Due to the nature of the research, we will seek a waiver of informed consent as has been done in similar pragmatic studies at our institutions.¹⁷⁻²¹

3.0 Previous Studies

From 2010 to 2012, our research team at Vanderbilt collaborated with two other sites to conduct the Centers for Disease Control and Prevention (CDC) funded Etiology of Pneumonia in the Community (EPIC) Study, a prospective, population-based surveillance study of community-acquired pneumonia hospitalizations in children and adults.^{2,22} We enrolled >2600 children, making EPIC the largest prospective study of pneumonia hospitalizations ever conducted in US children. Over 70% of children enrolled in EPIC had a viral pathogen detected whereas bacterial pathogens were identified in only 15% of children. Nevertheless, nearly 90% of children received antibiotics. In most cases, antibiotic treatment was discordant with the national guideline and broad-spectrum antibiotic use was common.²³ We have also evaluated the impact of the 2011 PIDS/IDSA guideline on antibiotic selection for children with pneumonia enrolled in EPIC, demonstrating only a modest reduction in the use of broad-spectrum antibiotics following publication of the guideline. Guideline-concordant use of narrow-spectrum aminopenicillins remained <20% by the end of the study, indicating a clear opportunity for further improvement.²³

We also used data from the EPIC study to develop a prognostic tool for assessing pneumonia disease severity in children. Prognostic tools use statistical modeling to combine inputs, such as demographics, clinical variables, and results of diagnostic tests, to produce reliable and unbiased risk estimates for a specified outcome. For our prognostic tool, we focused on acute in-hospital outcomes, organized into an ordinal severity scale consisting of 3 levels: severe, moderate, and mild. Our modeling strategy, ordinal logistic regression, offers increased statistical power and precision compared to binary/multinomial logistic regression, and the resulting output allows one to simultaneously estimate probabilities for each level on the outcome scale or in combination (e.g., probability of moderate to severe and probability of severe outcomes). Predictor variables for our prognostic tool were selected a priori and also informed by clinical expertise and literature review. We focused on objectively defined variables with strong hypothesized associations with the outcome that could be rapidly ascertained at presentation in the

clinical setting. This process resulted in a pool of 20 predictors. We also created a separate, more parsimonious model restricted to 9 predictors commonly available within electronic health records (EHR).

Both models accurately identified risk for moderate or severe pneumonia, indicating strong potential to improve risk stratification. Model discrimination, which measures the degree of concordance between observed and predicted outcomes, was excellent with a c-index ranging from 0.78-0.81. Differences in model fit and quality were considered negligible, and results from the internal bootstrap validation were comparable to the primary models. In the full model, PaO₂:FiO₂ ratio (PF ratio, estimated from the SaO₂:FiO₂ ratio),²⁴ age, heart and respiratory rates, altered mental status, temperature, chest indrawing, infiltrate pattern, and systolic blood pressure were the strongest predictors, contributing 96% of the explainable outcome variation. The EHR model retained most of these predictors (omitting altered mental status, chest indrawing, and infiltrate pattern). Nonetheless, predictive performance of the EHR model equaled that of the full model. For the full model, the median predicted risk for moderate or severe pneumonia was 18% (IQR 9-32%) and for severe pneumonia 5% (3-11%).

Prognostic tools used in adults with pneumonia improve risk stratification and clinical decision making, but these tools are underutilized, indicating a need for improved implementation strategies. A number of prognostic tools have been developed to assist providers caring for adults with pneumonia,²⁵⁻³¹ and most have undergone external validation.^{26,32-42} The two best studied tools are the PSI and CURB-65,^{30,31} which were designed to predict 30-day mortality. Newer tools (e.g., SMART-COP and SCAP)^{26,27} have also been developed to predict acute in-hospital outcomes, including mechanical ventilation and shock. These tools have been used to safely increase the number of low-risk patients treated in the outpatient setting and improve guideline-concordant antibiotic management.⁴³⁻⁴⁷ As a result, their use in the management of adults with pneumonia in outpatient and inpatient settings is strongly recommended.²⁵ Nonetheless, several studies indicate these tools are often applied incorrectly or not used at all.^{15,48-50} Major barriers to clinical use include tool complexity (inability to recall parameters and inaccurate scoring or interpretation) and disruptions to provider workflow (suspension of patient care to calculate risk by hand or use of an electronic application outside of routine care).⁵¹ Failure to validate new tools and assess their impact in new populations are also major impediments to clinical use. Each of these barriers must be carefully addressed to ensure effective implementation of new prognostic tools.

Effective decision support facilitates the adoption of new evidence into practice and helps standardize management to improve care and optimize outcomes. Clinical decision support is intended to directly impact provider decision-making to improve the quality, safety, effectiveness, and efficiency of care by steering behavior toward evidence-based care and away from unnecessary or unproven practices. The availability of comprehensive EHRs has allowed for the development of increasingly complex decision support applications, including risk stratification using real-time electronic capture of patient demographics, physiologic data, and diagnostic testing results.^{17,52} In a randomized trial conducted in primary care settings comparing decision support integrated with 2 prognostic tools vs. usual care without decision support, McGinn and colleagues showed a 25% reduction in antibiotic use overall and a 50% reduction in broad-spectrum antibiotic use in adults with possible bacterial pharyngitis or pneumonia when using the decision support application.⁵² The application was triggered on chief complaint and incorporated a risk calculator, which used automated and user-supplied inputs to identify risk for bacterial

pharyngitis or pneumonia, along with evidence-based treatment guidelines and order sets. In another study of adults with pneumonia presenting for emergency care within the Intermountain Healthcare System, Dean et al. showed increased guideline concordant care and reduced mortality in four different EDs using clinical decision support that included CURB-65 severity assessment and tailored recommendations for site of care, diagnostic testing, and antibiotic use compared to 3 usual care EDs.¹⁷ *These successful examples highlight the potential for EHR-based decision support to improve care by providing useful, evidence-based guidance at the point of care as management decisions are being made.*

Both Vanderbilt and the University of Pittsburgh have extensive experience leveraging EHR data for decision support and research purposes. As an example of such capabilities, in the EPIC study, a decision support tool used in adults with pneumonia was adapted for use as a screening tool.¹⁷ The tool used natural language processing to identify concepts suggestive of pneumonia in radiology “wet” reads in real-time and required a provider-confirmation of a pneumonia diagnosis. For EPIC, we adapted this tool to deliver electronic alerts to our enrollment teams. Importantly, a similar tool was used to identify pneumonia in the study by Dean et al. described in the preceding paragraph. A second example highly relevant to this proposal was developed by our co-investigator, [name], and involves antibiotic decision support to reduce inappropriate use of antibiotics in critically ill neonates. Importantly, the algorithm was followed in >70% of infants and led to significant reductions in antibiotic exposure.⁵³ Additionally, our co-investigators, Drs. [name] and [name], experts in human factors engineering and user-interface design of health information technology, possess extensive experience designing and evaluating decision support applications that maximize utility and minimize potential for human error.⁵⁴⁻⁶³ *These examples highlight that the investigators at Vanderbilt and the University of Pittsburgh possess the necessary skills, expertise, and institutional resources to develop and implement effective decision support applications.*

4.0 Study Design and Randomization

4.1 Study Design and Randomization (P1, EHR-based antibiotic decision support)

Effectiveness of the EHR-based antibiotic decision support application for promoting guideline-concordant antibiotic prescribing in children presenting for emergency care will be evaluated in a pragmatic, cluster randomized crossover study conducted over a period of 18 months that includes two respiratory seasons. Our institutions possess demonstrated experience in the execution of these pragmatic designs.¹⁷⁻²¹ Crossover will occur each month in a randomly determined sequence within each hospital. To ensure balanced representation of each arm in periods of both low and high pneumonia prevalence, randomization will occur in 3 permuted blocks (size=6). The cluster-randomized crossover design also improves efficiency and reduces potential problems related to cluster imbalance when using a small number of clusters.⁶⁷ The antibiotic decision support application will be provided to those randomized to the intervention arm, whereas the control arm will receive usual care. Due to the nature of the intervention, blinding of treating providers will not be possible. Importantly, since this is a trial focused on provider behavior, all children will receive standard of care management. All treatment decisions will be made by the clinical providers and will not be restricted or altered in any way.

4.2 Study Design and Randomization (P2, EHR-based risk stratification)

We will conduct a randomized controlled trial comparing our prognostic tool (intervention arm) to usual care (control arm) over a period of 24 months. Randomization will occur at the patient level. Allocation to intervention or control will be based on medical record number (even vs. odd) or similar strategy and will be assigned automatically once a provider confirms the diagnosis of pneumonia. Importantly, all standard of care treatment options will be available and decision-making will not be restricted in any way in either group. A similar randomized trial that predicts readmission risk among all hospitalized adults using EHR inputs is currently ongoing at Vanderbilt. In that study, every adult admitted to Vanderbilt University Hospital is enrolled (under waiver of consent). Readmission risk is calculated automatically for all patients, but only displayed for a random half to determine if providing this additional information improves outcomes compared to usual care.

5.0 Inclusion/Exclusion Criteria (Phases 1 and 2)

Inclusion Criteria

1. Six months to <18 years of age
2. Radiographic evidence of pneumonia in ED
3. Provider-confirmed diagnosis of pneumonia

Exclusion Criteria (Provider query and/or automated data abstraction)

1. Children with tracheostomy, cystic fibrosis, immunosuppression
2. Inter-hospital transfers
3. Hospitalization within preceding 7 days
4. Previously enrolled within preceding 28 days
5. Provider preference for any reason

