8.4 Power and Sample Size (P2)

As outlined in P1, we anticipate nearly 2000 children with pneumonia will be evaluated annually during the conduct of these studies. Assuming conservatively that data for 2000 children (1000 in each arm) are captured during the two-year study period, and 90% appropriate site of care disposition in the usual care arm (based on data from the EPIC cohort)²³, we will be able to detect an absolute difference of $\geq 3.4\%$ in appropriate care disposition at an alpha level of 0.05 with 80% power.

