### **6.3.2 Phase 2**

During the 24-month study period, randomization will occur at the patient level. Allocation to intervention or control will be based on medical record number (even vs. odd) and will be assigned automatically once the treating provider confirms the diagnosis of pneumonia and eligibility. We expect participants will be randomized (1:1). The providers of intervention subjects will receive prognostic information derived using our previously validated and best performing model. Providers of control arm subjects will not receive this information but will have access to all clinical data. Participants will be blinded to the treatment assignments and study staff and providers will not be blinded to treatment arm assignments due to the nature of the interventions.

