## **8 ANALYSIS POPULATIONS**

### **8.1 Intent-to-Treat (ITT) Population:**

The ITT Population includes any participant that is enrolled, randomized into the study. The ITT Population is the primary population for analysis unless otherwise stated.

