### **10.1 Primary Objective**

The primary objective (PO 1) of the study is to compare proportions of participants exclusively receiving guideline-concordant 1st line antibiotic therapy during the first 24 hours of care with or without EHR-based decision support in children 0.6-17 years of age presenting for emergency care. The hypothesis for this primary objective is that the proportion of participants exclusively receiving guideline-concordant 1st line antibiotic therapy during the first 24 hours of care is higher in the group receiving EHR-based decision support vs. the group receiving usual care. This information is captured through chart review and entered in the REDCap database. The antibiotics received by a participant is concordant yes (1) or no (0) based on Appendix 1 table, for this analysis.

The proportions will be compared between the intervention arm versus the control arm using a Cochran-Mantel-Haenszel method in a stratified analysis by site to control for two sites at the alpha 0.05 level. The proportion difference and corresponding 95% confidence interval for concordance of antibiotics with or without adjusting for sites will also be calculated.

We will use a hierarchical and mixed effects logistic regression model, a complex analytic approach which offers flexibility regarding model assumptions and incorporation of cluster-level and individual-level covariates. The outcome is proportions of participants exclusively receiving guideline-concordant 1st line antibiotic therapy during the first 24 hours of care and the main exposure variable is intervention vs. usual care. The month of each participant enrolled will be treated as a random effect. We will also use a weighted, cluster-level logistic regression to compare guideline-concordant antibiotic prescribing between groups. In this analysis, data for each cluster are collapsed into a single summary measure, and the summary measures are then analyzed as if they were raw data, facilitating simple data reporting and interpretation. Important baseline covariates (e.g., age, sex, race, site, season, frequency of bacteremia and other pneumonia-related complications) will also be assessed and included as model covariates.

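### Phase 2 lets a child enrol again after 28 days and record-number parity keeps every enrolment in one arm, but no Phase 2 analysis allows for repeat enrolments of the same child

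*Protocol*

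**What the plan says.** - **Re-entry.** Protocol section 5.0, which covers both phases, excludes a child "Previously enrolled within preceding 28 days". Nothing else in the criteria stops a later re-enrolment.
- **Allocation.** SAP 6.3.2 states: "Allocation to intervention or control will be based on medical record number (even vs. odd) and will be assigned automatically". Protocol 4.2 is looser: "Allocation to intervention or control will be based on medical record number (even vs. odd) or similar strategy".
- **Analysis set.** SAP 8.1: "The ITT Population includes any participant that is enrolled, randomized into the study". No rule says whether a child enrolled twice is one unit or two.
- **Phase 2 analyses.** SAP 11.1 makes the primary comparison with a Cochran-Mantel-Haenszel (CMH) test stratified by site at alpha 0.05, then a logistic model with robust errors for hospital. SAP 11.2 uses chi-square tests and logistic models clustered by hospital. SAP 11.3 uses a Wilcoxon test and a Cox model for length of stay.
- **Sample size.** Protocol 8.4 (repeated in SAP 6.2.2) assumes "data for 2000 children (1000 in each arm) are captured during the two-year study period". It takes a control rate of 90% and gives a detectable difference of 3.4 points at 80% power.

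No section of the SAP from the Introduction onward, and no section of the protocol, gives a first-enrolment rule, a child-level random effect or a child-clustered variance.

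**The concern.** A record number does not change between visits. Under the SAP rule the arm is therefore fixed for the child, not drawn afresh at each enrolment, and the child is in effect the unit of allocation. The tests take each enrolment as an independent observation.

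Two episodes in one child may share comorbidity, family circumstances and other stable features. If that makes their outcomes positively correlated, the correlation lies wholly within an arm and adds to the variance of the difference between arms. A test that ignores it then reports intervals that are too narrow and rejects a true null more often than 5% of the time. The unit of analysis is also left open, so two analysts could build different Phase 2 datasets from the same SAP.

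**Working it through.** **1. The plan's own figure.** Inputs from Protocol 8.4: 1000 per arm, 90% against 93.4%, alpha 0.05 (taken as two-sided). With the pooled-variance formula for two proportions, the mean proportion is 0.917:

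- null standard error = √(2 × 0.917 × 0.083 / 1000) = 0.01234
- alternative standard error = √((0.90 × 0.10 + 0.934 × 0.066) / 1000) = 0.01231
- z = (0.034 − 1.96 × 0.01234) / 0.01231 = 0.80, so power = 78.7%

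The difference detectable at 80% power is 3.45 points. The stated figure reproduces within rounding and contains no allowance for repeat children.

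**2. Variance with repeats in one arm.** Let r be the share of enrolments that are a child's second, with at most two per child, and ρ the within-child correlation of the outcome. Among N enrolments there are rN same-child pairs, each adding twice its covariance:

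- design effect DE = 1 + 2rρ
- true SE / computed SE = √DE
- effective n per arm = 1000 / DE
- true alpha of a nominal 0.05 test = 2 × (1 − Φ(1.96 / √DE))

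**3. Results.** Both r and ρ are assumptions. The simulated column is the size of the site-stratified CMH test under the null (8000 runs, 2000 enrolments, 90% rate); with no repeats it was 0.0505. Power is for 3.4 points at the effective n.

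| r | ρ | DE | SE ratio | Effective n per arm | True alpha | Simulated alpha | Power |
|---|---|---|---|---|---|---|---|
| 2% | 0.1 | 1.004 | 1.002 | 996 | 0.0505 | – | 78.6% |
| 5% | 0.3 | 1.03 | 1.015 | 971 | 0.0535 | 0.053 | 77.5% |
| 10% | 0.3 | 1.06 | 1.030 | 943 | 0.0570 | 0.054 | 76.4% |
| 10% | 0.5 | 1.10 | 1.049 | 909 | 0.0617 | 0.060 | 74.8% |
| 15% | 0.5 | 1.15 | 1.072 | 870 | 0.0676 | 0.066 | 72.9% |

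The Monte Carlo error of a simulated size near 0.05 is √(0.05 × 0.95 / 8000) = 0.0024, so simulation and formula agree, and the milder settings are hard to tell from 0.05.

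**4. What the power column assumes.** It takes 1000 per arm as enrolments. The protocol counts children. If 1000 distinct children per arm were reached, effective n would be 1000 / ((1 − r)(1 + 2rρ)): 1022 at 5% and 0.3, 1010 at 10% and 0.5. Power would then not fall, but the understated standard error and raised alpha would remain.

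**5. Phase 1.** Under the SAP's four-week periods, an enrolment more than 28 days later falls in another period. Within a permuted block of six, with three periods per arm, that period is in the same arm with probability 2/5 and the opposite arm with probability 3/5. Across blocks it is 1/2 each. The expected design effect within a block is 1 + 2rρ(2/5 − 3/5). At r = 10% and ρ = 0.5 this is 1 − 0.02 = 0.98. Across blocks it is 1.00.

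**6. Dropping repeats or keeping them.** First enrolments only leave 1000(1 − r) per arm; all enrolments, correctly analysed, are worth 1000 / (1 + 2rρ). At 5% and 0.3: 950 against 971. At 10% and 0.5: 900 against 909. At 15% and 0.5: 850 against 870. Keeping all is better whenever ρ < 1 / (2(1 − r)), hence for every ρ up to 0.5.

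**The case against.** The strongest case against is that the size is assumed. Neither r nor ρ appears in the documents. The Phase 2 outcome turns on the course of each separate episode (length of stay, ICU transfer, admission within 24 hours), so the correlation may be low, and covariates in the adjusted model may absorb part of it. This stands: the effect is modest, the last row of the table needs both extremes together, and with no positive correlation there is no understatement.

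Second, hospital-level robust errors formally cover children nested in hospitals. But with two clusters they are not reliable, and they do not apply to the CMH or chi-square tests.

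Third, the protocol's looser allocation wording could permit a fresh draw at each enrolment, which would spread repeats over both arms. The SAP names parity without an alternative, so the point holds for the plan as the SAP states it.

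A reader might infer more than the documents support:

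- **That every planned test in both phases treats enrolments as independent.** SAP 10.1 says "The month of each participant enrolled will be treated as a random effect" and adds a weighted cluster-level analysis. The month effect does not link a child's enrolments in different months, but step 5 shows no expected inflation.
- **That an earlier trial episode alters how a later one is scored in Phase 1.** SAP Appendix 1 has separate rows for prior beta-lactam exposure but gives no look-back window, so carry-over from a trial episode more than 28 days earlier is speculation.
- **That repeats should be removed from the primary set.** Step 6 shows this costs more information than the correlation does for ρ up to 0.5, and it narrows the ITT population.

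**Conclusion.** The concern holds for Phase 2. The plan permits repeat enrolment, the SAP's allocation rule keeps the repeats in one arm, and no Phase 2 analysis accounts for them. Whenever within-child correlation is positive, the standard errors are too small.

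The consequence is small over the range assumed. The direction is known if the correlation is positive; the amount cannot be derived from the documents, and the power loss depends further on how the 1000 per arm are counted. Because the planned size has no slack at 3.4 points and the correction is nearly free, it is worth making before the Phase 2 analysis.

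**What to change.** In SAP 11.1 to 11.3:

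1. State that the unit of analysis is the enrolment and that all enrolments stay in the ITT set.
2. Base the Phase 2 tests and confidence intervals on standard errors clustered on medical record number, with site as a covariate or stratum. For the primary outcome, this can be a regression on arm and site with a sandwich variance by record number in place of the unclustered CMH test. For length of stay, use the same clustering in the Cox model, and a rank test that allows for clustering or a bootstrap that resamples children.
3. Report the number of repeat enrolments by arm and site.
4. Give a first-enrolment-only analysis as a sensitivity analysis. In Phase 1 this is optional.

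Enrolment procedures do not change, and the record number already identifies repeats. The cost is slightly wider intervals and a little more analysis work.
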